**Specific Aim 2:**

**Primary Outcome:**

Attendance to Treatment: treatment attendance (defined as attending at least 1 or more visits with a mental health and/or substance use disorder (SUD) treatment provider during pregnancy and the postpartum year)

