## 1.0 Objectives / Specific Aims

### Specific Aim 1

The goal of Specific Aim 1 is to develop an effective remote mental health and substance use Screening, Brief Intervention and Referral to Treatment (SBIRT) program for pregnant and postpartum women. The **objectives** of this current application for Specific Aim 1 are to conduct a pilot RCT of a text-message based SBIRT and home-based telemedicine services for pregnant and postpartum women – called Listening to Women (LTW), compared to treatment as usual (TAU) with the primary objective to provide effect size estimates for a larger RCT.

**Specific Aim 1:** Conduct a pilot, small-scale randomized controlled trial to examine feasibility and preliminary efficacy of LTW, compared to TAU. Outcomes related to feasibility include percentage of eligible patients recruited, **study attrition**, **study retention**, and mental health and substance use treatment appointment attendance. Outcomes related to **preliminary efficacy** will include participation in screening, referral and treatment at baseline, compared to TAU.

The central hypotheses for Specific Aim 1 are that the study is feasible and women assigned to LTW will be more likely to screen positive and successfully obtain treatment in less time, compared to those that are assigned to TAU.

### Specific Aim 2

Upon completion of Specific Aim 1, the goal of Specific Aim 2 is to evaluate the effectiveness of a remote mental health and substance use Screening, Brief Intervention and Referral to Treatment (SBIRT) program for pregnant and postpartum women. The **objectives** of this current application for Specific Aim 2 are to conduct an RCT of a text-message based SBIRT and home-based telemedicine services for pregnant and postpartum women – called Listening to Women (LTW), compared to treatment as usual (TAU) with the primary objective to include attendance to treatment at baseline, compared to TAU.

**Specific Aim 2:** Conduct a randomized controlled trial to examine the effectiveness of LTW, compared to TAU. Outcomes related to **effectiveness** include attendance to treatment at baseline, compared to TAU.

The central hypotheses are that a greater proportion of women assigned to LTW will attend treatment following a referral, compared to TAU.

### Specific Aim 3

The goal of Specific Aim 3 is to gather data related to maternal and newborn diagnosis codes, health care utilization, and costs for our study participants with Medicaid.

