To address these barriers we designed, implemented and piloted LTW in routine perinatal care in one obstetric practice (see 3.0 Intervention to be Studied) as part of a quality improvement project. Our pilot demonstrates high rates of participation with 87.78% (273/311) of women approached agreeing to take part in LTW and completing the text-message screening. Preliminary data comparing LTW (N=273) to a historical dataset extracted from the EHR including peripartum women receiving in-person SBIRT in the same clinic (N=2,988) found a significantly greater proportion of women enrolled in LTW screened positive (81.15% vs. 33.33%;  $\chi^2=169.50$ ,  $p<0.0001$ ), were referred for treatment (76.12% vs. 57.63%;  $\chi^2=18.03$ ,  $p<0.0001$ ), and received treatment (94.91% vs. 16.04%;  $\chi^2=245.41$ ,  $p<0.0001$ ), compared to women receiving in-person SBIRT.

While these preliminary data are exciting, a randomized control trial will be necessary to determine the feasibility and efficacy of LTW. The goal of Specific Aim 1 is to examine the feasibility and preliminary efficacy of the proposed RCT methodology. Specific Aim 1 will inform Specific Aim 2 to then conduct a larger-scale RCT that examines LTW, compared to a control condition. This will allow us to identify and address barriers in recruitment, retention, use of LTW, and other procedures essential to successful conduct of the RCT. This approach is consistent with expert recommendations to use pilot mechanisms to test the feasibility of doing a full-scale RCT, use data yielded by the pilot study to “de-bug” the methodology, and to assess optimal strategies to executing the RCT [51- R34].

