## 4.0 Study Endpoints

### Specific Aim 1:

#### **Primary pilot efficacy outcome variables include:**

Completion of SBIRT: We will compare the proportion of participants that complete a screen for mental health and substance use, the proportion of those screening positive that are referred to treatment, and the proportion of those referred to treatment that had at least one mental health and/or substance use disorder treatment appointment among those assigned to LTW, compared to TAU.

Time to Treatment: We will measure the time from completion of screening positive to time of first mental health or substance use treatment appointment (if a referral to treatment was appropriate) among those assigned to LTW, compared to TAU.

Reduction in Mental Health Symptoms: Among women referred for treatment, we will compare the mean change in the Edinburgh Postnatal Depression Scale (EPDS) among those assigned to LTW, compared to TAU. *Of note, the suicidal ideation question (item #10) will be omitted from this questionnaire.*

Reduction in Substance Use: Among women referred for treatment, we will compare change in substance use frequency and amount as measured by the NIDA-Modified Assist (see LTW protocol) among those assigned to LTW, compared to TAU.

Improved Maternal Functioning: Among women referred for treatment, we will compare the change in maternal functioning measured by the Medical Outcomes Study Short Form 36 (SF-36v2) among those assigned to LTW, compared to TAU.

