**Secondary Outcomes**

Reduction in Mental Health Symptoms: Among women referred for treatment, we will compare the mean change in the Edinburgh Postnatal Depression Scale (EPDS), GAD-7 Anxiety and CSSRS among those assigned to LTW, compared to TAU. *Of note, the suicidal ideation question (item #10) will be omitted from the EPDS questionnaire.*

Reduction in Substance Use: Among women referred for treatment, we will compare change in substance use frequency and amount as measured by the NIDA-Modified Assist (see LTW protocol) and TLFB among those assigned to LTW, compared to TAU.

Improved Maternal Functioning: Among women referred for treatment, we will compare the change in maternal functioning measured by the Medical Outcomes Study Short Form 36 (SF-36v2) among those assigned to LTW, compared to TAU.

Improved Health-Related Social Needs: Among women referred for treatment, we will compare the change in health-related social needs measured by the Accountable Health Communities (AHC) Health-Related Social Needs (HRSN) Screening Tool among those assigned to LTW, compared to TAU.

For the outcome variables for specific aims 1 and 2 we will collect data from the EHR including SBIRT data, if the participant was referred to treatment, where they were referred to treatment, if they attended a mental health or substance use treatment appointment and where they attended the appointment, how many appointments they attended, and the numbers of days from date of SBIRT completion to date of mental health or substance use treatment appointment.

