## **5.0 Inclusion and Exclusion Criteria/ Study Population**

Inclusion criteria include: 1) age 18-41; 2) currently pregnant or postpartum; 3) if pregnant, receiving prenatal care; 4) English fluency; 5) owner of a cell phone with SMS text-message based capability; 6) access to WIFI and a device to allow audio and video teleconferencing; 7) able to provide informed consent. Exclusion criteria: None

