## **8.0 Recruitment Methods**

Recruitment will occur remotely, in person and via the EHR. A Research Data Request will be submitted to obtain a recruitment report of MUSC patients who potentially meet eligibility criteria. The recruitment report will include a search for pregnant and postpartum women. The report will include mrn, age, race, ethnicity, date of prenatal care visit, date of postpartum visit, delivery date, ob/gyn provider name, MyChart account (Yes/No), cell phone number, email address and current ICD-9 or 10 diagnoses. The purpose of the ICD codes will be to ensure we are approaching enough women with substance use disorders, and/or a mood or anxiety disorder diagnoses, and therefore likely to screen positive on either an in-person or text-message SBIRT screening. In addition, ICD codes will be used for urn stratification at randomization. Any patients who have not opted out of being contacted for research will be contacted by phone call or text message and invited to participate. If a cell phone number is not available, the message with a link to a RedCap eligibility survey will be sent via email or MyChart message. The study team will not cold-contact any patients who have chosen to opt-out of receiving contact about research or who have met the maximum number of contact attempts at the time of recruitment. Our PI's clinic policy is to ask all patients if they would like to be contacted for research opportunities and if they prefer to be contacted by phone or text message. The vast majority of women prefer to be contacted through a text message. Therefore, we believe cold-contacting patients via text is acceptable for this study. All other patients will be contacted through their providers to be informed of the study if the provider feels it is appropriate. If the potential participant's provider has agreed to have the study team contact their patient, a phone call or text message will be sent to the potential participant inviting them to take part in the study. If a cell phone number is not available, the message with a link to a RedCap eligibility survey will be sent via email. If the potential participant does not respond to the phone call, text or email, the study team may also notify potential participants that a message was sent to them via MyChart. The text message (or email/MyChart message) will include a link to a brief RedCap eligibility survey. For those meeting the eligibility screening criteria, the RA/RC will schedule a time to verify eligibility criteria and review the informed consent either remotely or in-person.

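### The Aim 2 primary outcome window follows the pregnancy, not randomisation, and neither the protocol's objectives nor the SAP settles when attendance starts to count

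*Protocol*

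**What the plan says.** - Protocol 4.0, Specific Aim 2, Primary Outcome: treatment attendance is "attending at least 1 or more visits with a mental health and/or substance use disorder (SUD) treatment provider during pregnancy and the postpartum year". Randomisation and referral are not mentioned.
- Protocol 1.0, Specific Aim 2, objective: "the primary objective to include attendance to treatment at baseline, compared to TAU".
- Protocol 1.0, Specific Aim 2, hypothesis: "a greater proportion of women assigned to LTW will attend treatment following a referral, compared to TAU".
- Protocol 4.0, list of EHR data for Aims 1 and 2: "the numbers of days from date of SBIRT completion to date of mental health or substance use treatment appointment". This is an item to be extracted, not a definition of the outcome.
- SAP, Sample Size and Power Analysis: attended treatment is powered at 2.1% (usual care, n=191) versus 8.3% (LTW, n=224). The usual-care rates are said to come from earlier work on the programme. The SAP states no start, no end and no handling of care already under way.
- Protocol 5.0 admits women who are pregnant or postpartum at any stage, with "Exclusion criteria: None". Protocol 8.0 uses diagnosis codes to "ensure we are approaching enough women with substance use disorders, and/or a mood or anxiety disorder diagnoses", and recruits on the mother-baby unit and in the investigators' own practices.

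**The concern.** The definition as written includes time before assignment. A woman who saw a mental health provider early in pregnancy and was randomised after delivery is already a success, whichever arm she joins. No section says that such visits count, and none excludes them. The objective and the hypothesis point to different timings, so three readings of one primary outcome are open.

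Two things are at stake. A primary outcome without a time origin leaves the window to be settled at analysis. And if earlier visits are counted, they add similar successes to both arms. The absolute difference shrinks only slightly, but the relative risk and the power of the planned chi-square test fall faster, because the planned usual-care rate is so low. Earlier visits are plausible here, given open entry and the effort to reach women with existing diagnoses.

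**Working it through.** **1. The SAP's power figure.** Inputs: 2.1% and 8.3%, n = 191 and 224, two-sided 5%. Power = Φ[(d − 1.96·s0)/s1], where s0 is the pooled and s1 the unpooled standard error.
- d = 0.062; pooled rate = (191×0.021 + 224×0.083)/415 = 0.0545; s0 = 0.02235; s1 = 0.02115.
- (0.062 − 0.0438)/0.02115 = 0.86, so power is 80.5%. The stated 80% is reproduced.

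**2. Which outcome the 2.1% describes.** Protocol 2.0 reports, for in-person SBIRT, 33.33% screened positive, 57.63% referred and 16.04% treated. Starting from the SAP's 65.2% screened under usual care:
- 65.2% × 33.33% = 21.7% (SAP, screened positive: 21.7%)
- 21.7% × 57.63% = 12.5% (SAP, referred: 12.5%)
- 12.5% × 16.04% = 2.0% (SAP, attended: 2.1%; 4/191 is also 2.1%)

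So the planning rate looks like attendance at the end of the screening and referral cascade. That is how the Aim 1 outcome is framed: "the proportion of those referred to treatment that had at least one mental health and/or substance use disorder treatment appointment". It may differ from the rate of any visit in the Aim 2 window.

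**3. Dilution if earlier visits count.** Let q be the share of women in each arm with a qualifying visit before randomisation (assumed; not in the documents). Usual-care rate = q + (1−q)×0.021; LTW rate = q + (1−q)×0.083.

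| q | Usual care | LTW | Difference (points) | RR | Power at 191/224 |
|---|---|---|---|---|---|
| 0% | 2.1% | 8.3% | 6.2 | 3.95 | 81% |
| 1% | 3.1% | 9.2% | 6.1 | 2.99 | 73% |
| 2% | 4.1% | 10.1% | 6.1 | 2.50 | 66% |
| 5% | 7.0% | 12.9% | 5.9 | 1.84 | 51% |
| 10% | 11.9% | 17.5% | 5.6 | 1.47 | 35% |

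**4. Sensitivity to the LTW rate.** With LTW at 15% instead of 8.3% and q = 10%, the rates are 11.9% and 0.10 + 0.90×0.15 = 23.5%. Power is Φ[(0.1161 − 1.96×0.03797)/0.03676] = Φ(1.13) = 87%.

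**5. What a date rule recovers.** Suppose a share c of women with earlier visits attend again after randomisation whatever their arm, and the others behave like everyone else. The usual-care rate is then qc + (1−qc)×0.021, so qc takes the place of q in step 3. At q = 10%:
- none continue: 2.1%, power 81%
- half continue: 7.0%, power 51%
- all continue: 11.9%, power 35%

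Simulation of the same settings (200,000 trials each, chi-square without continuity correction) gave 83/51/36%. A Mantel-Haenszel test stratified by earlier visit gave 83/63/79%.

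**6. Why the SBIRT interval cannot supply the start.** A woman who never completes SBIRT has no such interval. At the SAP's example rates that is 100 − 65.2 = 34.8% of usual care and 100 − 77.7 = 22.3% of LTW.

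**The case against.** The strongest reply is that this is a wording fault and that the intended outcome is visible. The hypothesis speaks of attendance after referral, the planning rate is consistent with that, and the SBIRT interval could help to screen out earlier visits. If analysts count only visits after referral, the dilution does not arise. That stands, and it is why the power table is only an illustration.

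The table also rests on two assumptions made together. The 8.3% is the smallest rate detectable against 2.1%, not a forecast, so the table starts at 80% power and any dilution looks severe. And high values of q are unsupported. Protocol 2.0 puts identification below 50% and treatment among those identified below 15%, so under 0.50×0.15 = 7.5% of women with a mental illness are treated, or about 1% of all women at a prevalence of 1 in 7. Targeted recruitment could raise this, but Protocol 10.0 says that recruitment is mainly remote through the EHR. Both points stand.

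Three stronger readings are tempting but unsupported:
- The SBIRT interval contradicts the primary definition. It is a data item with its own time origin.
- The SAP's power calculation is wrong, or 2.1% is known to be the wrong rate. The arithmetic reproduces. Step 2 is an inference, and no document gives a window for the historical 16.04% or an any-visit rate.
- Earlier visits favour one arm. Within one allocation period, randomisation balances them in expectation. The change of allocation ratio in Protocol 10.0 is a separate matter.

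None of this gives the outcome a start date.

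**Conclusion.** The point holds as a flaw in a stated rule. The only working definition of the primary outcome admits events before assignment, the objectives give two other timings, and the SAP does not choose between them. It should be fixed; confidence is medium.

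The effect on power cannot be stated from the documents. At the detectable LTW rate it runs from nothing (q = 0, or only visits after referral counted) to a fall from 81% to 35% at q = 10%. A reader might infer that the trial is underpowered. The documents do not support that, because q and the true LTW rate are unknown and the rule that analysts will apply is unstated.

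**What to change.** Use one definition in Protocol 1.0, Protocol 4.0 and the SAP: at least one mental health or SUD visit dated after randomisation through the end of the postpartum year, among all randomised women, under the same rule in both arms. Do not make it conditional on SBIRT completion or referral. Both follow assignment, and the SAP itself compares the arms on them (referral, for example, 12.5% versus 23.1%). Extract visit dates relative to randomisation, and restate or justify the usual-care planning rate for this window.

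The cost is wording, a restated rate and a small addition to an EHR extraction already planned. There are two downsides. Care that continues after randomisation still counts in both arms, so the date rule alone may recover little power if most women with earlier visits carry on (step 5). Follow-up length will also still vary with time of entry.

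Optional: record earlier visits from the EHR as a baseline variable and pre-specify a supporting analysis stratified by it.

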**Secondary Outcomes**

Reduction in Mental Health Symptoms: Among women referred for treatment, we will compare the mean change in the Edinburgh Postnatal Depression Scale (EPDS), GAD-7 Anxiety and CSSRS among those assigned to LTW, compared to TAU. *Of note, the suicidal ideation question (item #10) will be omitted from the EPDS questionnaire.*

Reduction in Substance Use: Among women referred for treatment, we will compare change in substance use frequency and amount as measured by the NIDA-Modified Assist (see LTW protocol) and TLFB among those assigned to LTW, compared to TAU.

Improved Maternal Functioning: Among women referred for treatment, we will compare the change in maternal functioning measured by the Medical Outcomes Study Short Form 36 (SF-36v2) among those assigned to LTW, compared to TAU.

Improved Health-Related Social Needs: Among women referred for treatment, we will compare the change in health-related social needs measured by the Accountable Health Communities (AHC) Health-Related Social Needs (HRSN) Screening Tool among those assigned to LTW, compared to TAU.

For the outcome variables for specific aims 1 and 2 we will collect data from the EHR including SBIRT data, if the participant was referred to treatment, where they were referred to treatment, if they attended a mental health or substance use treatment appointment and where they attended the appointment, how many appointments they attended, and the numbers of days from date of SBIRT completion to date of mental health or substance use treatment appointment.

**Specific Aim 3:**

The data that will be collected on study participants with Medicaid include:

Number and costs of prenatal care visits

Number and costs of postpartum care visits

Number and costs of hospitalizations during pregnancy and the postpartum year

Number and costs of ED visits during pregnancy and the postpartum year

Number and costs of newborn care visits (outpatient, inpatient and ED) in the first year of life

Maternal diagnosis codes for prenatal care visits, postpartum care visits, hospitalizations and ED visits

Newborn diagnosis codes for outpatient, inpatient and ED visits

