**Specific Aim 3:** We will compare Medicaid data among those assigned to LTW vs. TAU.

The central hypothesis is that those assigned to LTW will have lower health care utilization and costs during the postpartum year, compared to TAU.

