
Another method of recruitment will include Women's Health Services clinics, where after women are identified as pregnant or postpartum by the patient's nurse or provider, they will be approached by the study team, with the provider's permission, to take part in the study. Additionally, research staff may do a review of Women's Health Services provider schedules and patient charts in EPIC to identify potentially eligible women for inclusion. Research staff will approach patients when they arrive for their regularly scheduled appointment.

We will also recruit from the MUSC antepartum unit and the mother-baby unit. Patients will be approached by the study team, with the provider's permission, to take part in the study. Additionally, research staff may do a review of the antepartum and mother-baby unit schedules and patient charts in EPIC to identify potentially eligible women for inclusion. Research staff will approach patients while they are staying on the antepartum and mother-baby units. If the patient agrees to taking part in the study the RA will consent the participant and complete baseline procedures.

Another way to recruit is the potentially eligible patients in the PI and Co-Is practices will be informed and approached about the study as the PI and Co-Is feel is appropriate. Participants will also be recruited via study advertisement (e.g., flyers) and online postings (e.g., social media, linkedin).

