\*\*Only participants in specific aim 2 complete the GAD-7, CSSRS and TLFB

\*\*\*Only participants assigned to LTW will complete the usability scale

+ As of the approval of amendment 10 newly enrolled participants will not complete CSSRS and TLFB. Participants consented prior to the approval of amendment 10 will complete CSSRS and TLFB at baseline.

Specific aim 3: We will gather healthcare utilization data on our study participants who have Medicaid insurance. The MUSC study team will extract the maternal Medicaid IDs from our study participants with Medicaid insurance from the EHR. We will share a list of these maternal Medicaid IDs with Medicaid, and they will return data related to maternal and newborn diagnosis codes, health care utilization and costs for these participants i.e., prenatal care visits, postpartum care visits, hospitalizations and ED visits during pregnancy and the postpartum year. The MUSC study team will send the maternal Medicaid ID's of study participants to Medicaid in a password protected spreadsheet. Medicaid will send the MUSC study team a password protected spreadsheet of data. The spreadsheet of data Medicaid will send back to MUSC will be coded since

it will contain the Medicaid ID's of participants.

The Medicaid ID is the only link to subjects in the study. The document linking Medicaid ID's and our study participants will be stored on a University secure network drive or in MUSC BOX. The linking document will be stored separately from the study data and only trained study personnel will have access to the linking document.

Study data will be stored on a University secure network drive or in MUSC BOX. The spreadsheet of data that Medicaid will send the MUSC study team will be password protected. Only trained study personnel will have access to the password protected data spreadsheet.

The MUSC study team will have access to the Medicaid ID's as well as Medicaid.

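### Aim 3 has two unreconciled time windows, neither starting at randomisation, so Medicaid use from before randomisation can enter the LTW versus TAU comparison

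*Protocol*

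**What the plan says.** Three places in the protocol bear on the Aim 3 window.

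- **Hypothesis (1.0, Specific Aim 3):** "those assigned to LTW will have lower health care utilization and costs during the postpartum year, compared to TAU".
- **Items (4.0, Specific Aim 3):** "Number and costs of hospitalizations during pregnancy and the postpartum year" and "Number and costs of ED visits during pregnancy and the postpartum year", together with "Number and costs of prenatal care visits", which has no start date. Newborn visits are listed for the first year of life. The list is introduced as data to be collected.
- **Data return (10.0, Specific aim 3):** Medicaid is to supply "prenatal care visits, postpartum care visits, hospitalizations and ED visits during pregnancy and the postpartum year".

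Entry is open to anyone "currently pregnant or postpartum" (5.0), with no gestational or postpartum limit. Section 8.0 adds inpatient recruitment: "We will also recruit from the MUSC antepartum unit and the mother-baby unit". Under 10.0, randomisation takes place at baseline, after consent.

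The SAP treats every outcome as dichotomous. It gives no method, window, offset or covariate for counts or costs. The only mention of adjustment is in protocol section 12.0 (Quality Assurance). It is conditional on how baseline characteristics compare between arms, and it does not name prior use.

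**The concern.** An outcome in a randomised comparison should begin at randomisation, because use that came earlier cannot have been affected by the assigned arm. Neither Aim 3 window is tied to that date.

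On the wider span, a woman recruited on the mother-baby unit brings all her prenatal visits and the start of her delivery stay into the outcome. A woman recruited on the antepartum unit brings in the admission during which she was recruited. On the hypothesis window both examples largely disappear, but a woman randomised some months after delivery still has part of her year behind her.

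What is at stake is the sensitivity of the Aim 3 comparison. Any ratio of use or cost shrinks towards 1, and any absolute difference carries extra variance. With two windows in the protocol and no Aim 3 analysis in the SAP, the choice between them could also be made after the data are seen.

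**Working it through.** **Plan's own figure.** None exists for Aim 3: no sample size, power, effect, standard deviation or Medicaid share is stated. The SAP's power figures concern the dichotomous outcomes only. Everything below is illustration.

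**From the documents.** The two windows (1.0 against 4.0 and 10.0), entry at any time in pregnancy or postpartum (5.0), and randomisation at baseline (10.0).

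**Assumptions.** Pregnancy of 40 weeks and a postpartum year of 52 weeks, so 92 weeks in all; constant rate of use; true rate ratio of 0.80 after randomisation; variance proportional to time; correlation r between pre- and post-randomisation use of 0 to 0.5.

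**Step 1. Dilution of a ratio.** Let f be the share of the window that precedes randomisation. Then

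observed ratio = 1 − 0.20 × (1 − f).

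If use is not constant, f should be read as the share of use, not of time.

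**Step 2. Hypothesis window (52 weeks).** For any woman randomised in pregnancy f = 0, and the ratio stays at 0.80. For later entry:

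| Entry | f | Ratio seen |
|---|---|---|
| 6 weeks postpartum | 6/52 = 12% | 0.82 |
| 12 weeks postpartum | 12/52 = 23% | 0.85 |
| 26 weeks postpartum | 26/52 = 50% | 0.90 |

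The newborn's first year gives the same shares when the mother is randomised after the birth.

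**Step 3. Wider span (92 weeks).**

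| Entry | f | Ratio seen |
|---|---|---|
| Gestational week 12 | 12/92 = 13% | 0.83 |
| Gestational week 20 | 20/92 = 22% | 0.84 |
| Gestational week 28 | 28/92 = 30% | 0.86 |
| Delivery | 40/92 = 43% | 0.89 |
| 12 weeks postpartum | 52/92 = 57% | 0.91 |
| 26 weeks postpartum | 66/92 = 72% | 0.94 |

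**Step 4. Precision of an absolute difference.** With s = √(f/(1 − f)), the SD of the window total relative to the SD of post-randomisation use alone is √(1 + s² + 2rs).

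- *Hypothesis window, r = 0.* The variance factor is 1 + s² = 1/(1 − f). This is 1.13, 1.30 and 2.00 for entry at 6, 12 and 26 weeks postpartum, and larger for positive r.
- *Wider span, all entering at gestational week 20.* s² = 0.217/0.783 = 0.278, and the SD factor is 1.13, 1.26 and 1.34 for r = 0, 0.3 and 0.5. If an analysis of post-randomisation use had 80% power, the window total would have about 70%, 60% and 55%.
- *Post-randomisation use adjusted for prior use.* The variance factor is 1 − r² = 1, 0.91 and 0.75, which gives power of 80%, 84% and 90%.

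**Step 5. Whole sample, hypothesis window.** The share of Medicaid participants randomised after delivery is not given. If it were 10% to 50%, spread evenly over the year (so mean f = 0.5 and ratio 0.90 in them), the overall ratio would be 0.10 × 0.90 + 0.90 × 0.80 = 0.81, up to 0.50 × 0.90 + 0.50 × 0.80 = 0.85. The documents do not support an even spread. Section 10.0 describes a weekly search for new patients and section 8.0 adds the mother-baby unit, either of which could bring entry closer to delivery.

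**The case against.** The strongest reply is that sections 4.0 and 10.0 describe a data pull, not an analysis. The one stated comparison window is the postpartum year, and for maternal use that year lies wholly after randomisation for every woman enrolled in pregnancy, and almost wholly for those enrolled on the mother-baby unit. This stands, and it confines the dilution on the hypothesis window to women randomised well after delivery, whose number is not given. It does not dispose of the point: the list sits under Study Endpoints and is the only Aim 3 endpoint text, and nothing says which window governs.

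Secondly, randomisation balances earlier use in expectation, so an absolute difference in mean counts or costs is not biased by including it. This also stands. Only ratios shrink; differences lose precision. One qualification is that section 10.0 reverses the Aim 2 allocation from 2:1 to 1:2, so the balance holds within each allocation period. The documents do not say whether entry timing changed between periods.

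Thirdly, collecting pregnancy data is what makes a prior-use covariate possible. A reader might infer that this covariate has been thrown away. The documents do not support that: it is unspecified, not excluded, and section 12.0 leaves room for adjustment. Its value will also vary, since a woman enrolled early in pregnancy has little earlier use in a file that begins with the pregnancy.

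**Conclusion.** The point holds as one of specification with a calculable consequence. Aim 3 has two windows that do not agree, neither begins at randomisation, and no analysis chooses between them. Following the item list as written would bring use that LTW cannot affect into the outcome for nearly every woman. Following the hypothesis would do so only for women randomised after delivery, where a true ratio of 0.80 would appear as 0.82 to 0.90 for entry between 6 and 26 weeks postpartum. That range rests on constant use and an illustrative effect.

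A reader might infer that the trial has chosen to count use over the whole span, so that every Aim 3 result will be diluted, or that half the postpartum year is lost on average. Neither follows. The item list is introduced as data collection, the hypothesis is narrower, and nothing in the documents shows postpartum entry spread evenly over the year. The overall loss cannot be stated without entry timing, the Medicaid share and the correlation between earlier and later use.

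**What to change.** 1. **Reconcile** sections 1.0, 4.0 and 10.0, so that one window is named for the Aim 3 hypothesis and the wider data list is labelled as collection only.
2. **Maternal use and costs for the hypothesis:** count from the later of randomisation or delivery discharge, leaving out any stay in progress at randomisation, to the end of the postpartum year. This keeps the delivery stay from counting only for women enrolled before birth.
3. **Newborn use and costs:** count from the later of birth or randomisation to the end of the first year.
4. **Model:** use a person-time offset and adjust for pregnant versus postpartum at entry. The offset alone assumes comparable rates throughout, and the birth stay counts only for newborns whose mothers were randomised before delivery.
5. **Pregnancy-period comparison:** report it separately, from randomisation to delivery, among women randomised in pregnancy.
6. **Covariates:** pre-specify use and cost before randomisation from the same Medicaid file. Use between randomisation and delivery is post-randomisation and should not be adjusted for.

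**Cost.** SAP wording and aligned protocol text, with no new data source and no further contact with participants. The Medicaid return must carry service dates. The documents do not say that it will, so the data request may have to change if only totals are planned. Prior-use data will be sparse for women enrolled early in pregnancy, so the gain in precision from item 6 will be uneven. The window should be fixed before the arms are compared.
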